6.1 DEFINITIONS

6.1.1 Adverse Event

An adverse event is defined as any reaction, side effect, or untoward event that occurs during the course of the clinical trial associated with the research in humans, whether or not the event is considered related to the treatment or clinically significant. For this study, AEs will include

events reported by the patient, as well as clinically significant abnormal findings on physical examination or laboratory evaluation. A new illness, symptom, sign or clinically significant laboratory abnormality or worsening of a pre-existing condition or abnormality is considered an AE.

All AEs, including clinically significant abnormal findings on laboratory evaluations, regardless of severity, will be followed until return to baseline or stabilization of event. Serious adverse events that occur more than 30 days after the last study procedure and have an attribution of at least possibly related to the agent/intervention should be recorded and reported as per section 6.2.

6.1.2 Unexpected adverse reaction

An adverse event or suspected adverse reaction is considered “unexpected” if it is not listed in the investigator brochure or is not listed at the specificity or severity that has been observed; or, if an investigator brochure is not required or available, is not consistent with the risk information described in the general investigational plan or elsewhere in the current application.

6.1.3 Serious

An Unanticipated Problem or Protocol Deviation is serious if it meets the definition of a Serious Adverse Event or if it compromises the safety, welfare or rights of subjects or others.

6.1.4 Serious Adverse Event

An adverse event or suspected adverse reaction is considered serious if in the view of the investigator or the sponsor, it results in any of the following:

- Death,
- A life-threatening adverse experience
- Inpatient hospitalization or prolongation of existing hospitalization
- Persistent or significant incapacity or substantial disruption of the ability to conduct normal life functions
- A congenital anomaly/birth defect.
- Important medical events that may not result in death, be life-threatening, or require hospitalization may be considered a serious adverse drug experience when, based upon appropriate medical judgment, they may jeopardize the patient or subject and may require medical or surgical intervention to prevent one of the outcomes listed in this definition.

6.1.5 Disability

A substantial disruption of a person’s ability to conduct normal life functions.

6.1.6 Protocol Deviation (NIH Definition)

Any change, divergence, or departure from the IRB approved research protocol.

6.1.7 Non-compliance (NIH Definition)

Abbreviated Title: Subclinical Hypercortisolism

Version Date: 12/19/2016

The failure to comply with applicable NIH Human Research Protections Program (HRPP) policies, IRB requirements, or regulatory requirements for the protection of human research subjects.

6.1.8 Unanticipated Problem

Any incident, experience, or outcome that:

- Is unexpected in terms of nature, severity, or frequency in relation to
 - (a) the research risks that are described in the IRB-approved research protocol and informed consent document; Investigator's Brochure or other study documents, and
 - (b) the characteristics of the subject population being studied; **AND**
- Is related or possibly related to participation in the research; **AND**
- Suggests that the research places subjects or others at a *greater risk of harm* (including physical, psychological, economic, or social harm) than was previously known or recognized.

6.2 NCI-IRB AND NCI CLINICAL DIRECTOR REPORTING

6.2.1 NCI-IRB and NCI CD Expedited Reporting of Unanticipated Problems and Deaths

The Protocol PI will report in the NIH Problem Form to the NCI-IRB and NCI Clinical Director:

- All deaths, except deaths due to progressive disease
- All Protocol Deviations
- All Unanticipated Problems
- All non-compliance

Reports must be received within 7 days of PI awareness via iRIS.

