- Thus, patients with subclinical hypercortisolism may benefit from operative intervention to halt or reverse metabolic complications associated with the disease and the risk of malignant progression.
- The optimal management of patients with subclinical hypercortisolism and adrenal incidentalomas is controversial and no large randomized trial has been conducted.
- We hypothesize that operative treatment would reduce the risk of long term complications of subclinical hypercortisolism and malignant progression, and propose a prospective randomized trial comparing nonoperative and operative management of subclinical hypercortisolism in patients with an adrenal neoplasm.

Objectives:**Primary Endpoints:**

- To determine whether unilateral adrenalectomy in patients diagnosed with subclinical hypercortisolism and adrenal neoplasm results in normalization and/or improvement of hypertension as assessed by reduction in pharmacotherapy and/or normalization of blood pressure (systolic pressure ≤ 140 and diastolic pressure ≤ 90), diabetes as assessed by reduction or elimination of pharmacotherapy and/or improvement in A₁C to $< 6.5\%$, osteoporosis by increase in bone formation markers indicative of increased bone formation, hypercholesterolemia as assessed by a reduction or elimination of pharmacotherapy and/or reduction in LDL levels to risk-stratified goal levels as defined by ATP III, and/or overweight or obesity as assessed by a 10 percent reduction in weight at 6 months.

Eligibility:

- An individual with an adrenal neoplasm less than 5 cm in size with biochemically confirmed evidence of hypercortisolism (2 out of 3: dexamethasone suppression test (DST) > 3 mcg/dL, elevated urine free cortisol, and/or morning ACTH < 2.2 pmol/l) without overt clinical signs and symptoms.
- Age greater than or equal to 18 years.
- Adults must be able to understand and sign the informed consent document.

Abbreviated Title: Subclinical Hypercortisolism

Version Date: 12/19/2016

- Patients must have laboratory and physical examination parameters within acceptable limits based on standard clinical practice.

Design:

- Prospective randomized study comparing adrenalectomy versus observation.
- Patients assigned to the operative arm will undergo adrenalectomy and then followed postoperatively for normalization and/or improvement of metabolic complications associated with hypercortisolism and histologic examination of the resected tumor.

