The natural history of subclinical hypercortisolism is associated with progression and consequences of metabolic diseases (3). Studies have shown that cortisol excess may lead to or contribute to long term consequences such as hypertension, diabetes, dyslipidemia, obesity, and osteoporosis (1, 14, 16). In these patients, hypertension has a prevalence of 33% to 89% (8-15, 17), diabetes and/or impaired glucose metabolism has a prevalence of 15 to 66% (8-15, 17, 18), dyslipidemia has a prevalence of 23 to 77% (8, 10-12, 14, 17-18), overweight and/or obesity has a prevalence of 19 to 75% (8, 10-12, 14), and osteoporosis has a prevalence of 30% (10).

Because of the high prevalence of cardiovascular disease in subclinical hypercortisolism in patients with a unilateral adrenal neoplasm some investigators have compared patients with subclinical hypercortisolism with a unilateral adenoma to patients with a nonfunctioning unilateral adrenal neoplasm to assess the consequences and contribution of increased cortisol secretion. A recent large cross-sectional study by Di Dalmazi, et. al., showed patients with subclinical hypercortisolism to have a higher prevalence of type 2 diabetes, coronary heart disease, osteoporosis, and fractures when compared to patients with nonfunctioning adrenal neoplasms. Over a ten year period, 348 eligible patients with an adrenal incidentaloma were included and divided into four groups consisting of patients with nonfunctional adenomas

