6.2.2 NCI-IRB Requirements for PI Reporting at Continuing Review

The protocol PI will report to the NCI-IRB:

1. A summary of all protocol deviations in a tabular format to include the date the deviation occurred, a brief description of the deviation and any corrective action.
2. A summary of any instances of non-compliance
3. A tabular summary of the following adverse events:
 - All Grade 2 **unexpected** events that are possibly, probably or definitely related to the research;
 - All Grade 3 and 4 events that are possibly, probably or definitely related to the research;
 - All Grade 5 events regardless of attribution;
 - All Serious Events regardless of attribution.

Abbreviated Title: Subclinical Hypercortisolism

Version Date: 12/19/2016

NOTE: Grade 1 events are not required to be reported.

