8.5 RISKS/BENEFITS ANALYSIS

The main risk of participation is related to the risk of complications in the adrenalectomy arm and worsening of the metabolic complications in patient in the observation arm. The risk of

Abbreviated Title: Subclinical Hypercortisolism

Version Date: 12/19/2016

adrenalectomy is less than 1% which would outweigh the potential benefit of reversal of metabolic complications. In patients in the observation arm, there may be worsening of the metabolic complications but all patients will cross over to the adrenalectomy arm after 6 months of follow up and will be medically treated as standard of care for the metabolic complications.

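### Section 6.2.1 exempts deaths from an undefined progressive disease, so a death attributed to the untreated condition may miss the mandatory 7-day report

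*Combined protocol and SAP*

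**What the plan says.** Section 6.2.1 lists what the principal investigator must send to the IRB and the Clinical Director on an expedited basis. For deaths the rule is "All deaths, except deaths due to progressive disease". The same list includes "All Unanticipated Problems", and the time limit is given as "Reports must be received within 7 days of PI awareness via iRIS".

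Other parts of Section 6 also bear on a death:

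- Section 6.1.8 defines an Unanticipated Problem by three conditions that must all be met. The first begins "Is unexpected in terms of nature, severity, or frequency in relation to" and refers to the research risks already described and to the characteristics of the population. The other two are possible relatedness to participation, and a suggestion of greater risk of harm than was known.
- Section 6.2.2 requires a table at continuing review that includes "All Grade 5 events regardless of attribution", and all serious events on the same basis.
- Section 6.3.1 says that any safety concern goes to the IRB immediately. It gives review of adverse event data to the principal investigator and describes no independent committee.

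The term *progressive disease* is not defined in the supplied text. Section 5.4.1 defines improvement in each metabolic complication, but not progression.

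**The concern.** An exception of this kind suits a trial in advanced cancer, where death from progression is an expected background event. Here Section 2.1 limits entry to masses under 5 cm and excludes confirmed adrenocortical carcinoma, pre-existing cancers or adrenal metastases, and imaging features that suggest malignancy.

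In this protocol, progression refers to the condition under study. Section 1.2 states: "The natural history of subclinical hypercortisolism is associated with progression and consequences of metabolic diseases". The Précis says that surgery may "halt or reverse metabolic complications associated with the disease and the risk of malignant progression". Section 8.5 sets the risk of surgical complications against "worsening of the metabolic complications in patient in the observation arm".

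At stake is how soon a body outside the research team is certain to learn of a death that bears on the safety of deferring surgery. The attribution that decides this is made by an investigator who knows the patient's arm.

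**Working it through.** No figure in the plan needs to be reproduced. The check sets the reporting rules side by side and follows two hypothetical deaths through them.

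**Step 1. What the exception could cover.** With no definition, two readings are open:

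- *Narrow:* tumour progression only. Known carcinoma is excluded, so this leaves a mass that proves malignant after entry. The Précis cites that risk, and Section 1.1.2 makes measuring it a secondary objective.
- *Wide:* progression of the hypercortisolism and its metabolic effects, in line with the natural history given in Section 1.2. Section 3.1 adds that metabolic worsening is not a ground for crossover, so an observed patient may remain in that state until month 6.

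On either reading, any death covered is one attributed to the condition under study.

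**Step 2. Two deaths, four routes.**

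| Route | Timing | Death from a surgical complication | Death attributed to the untreated condition |
|---|---|---|---|
| 6.2.1, deaths | 7 days | Mandatory | Exempt if classed as progressive disease |
| 6.1.8 and 6.2.1, Unanticipated Problem | 7 days | If all three conditions are judged met | If all three conditions are judged met |
| 6.3.1, safety concern | Immediately | If judged a concern | If judged a concern |
| 6.2.2, Grade 5 table | Continuing review | Yes | Yes |

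Only the first row differs between the two deaths, and it is the only expedited route for deaths that needs no finding of unexpectedness or concern.

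**Step 3. Does the Unanticipated Problem route close the gap?** Not reliably. Worsening under observation is a described risk, so a death from it may be judged expected in nature. Section 8.5 describes worsening, not death, so the death could still qualify as unexpected in severity. Either judgement can be defended.

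**Step 4. Scale, under stated assumptions.**

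- *Chance that the question arises during observation.* The documents give no mortality rate. If *m* is the 6-month risk of death from any cause, the chance of at least one death among 31 observed patients is 1 − (1 − *m*)^31. Taking *m* as 0.1%, 0.5%, 1%, 2% and 3% gives 3%, 14%, 27%, 47% and 61%. The chance of an exempt death is no higher than this, because only deaths attributed to progressive disease are exempt.
- *Patients randomised in the interval.* The interval between continuing reviews is not stated. Section 7 expects 15 to 20 patients a year and 31 per arm, so half go to observation. An assumed 12-month interval gives 15 × 1/2 = 7.5 to 20 × 1/2 = 10 further patients allocated to observation. A 6-month interval gives half of that, 3.75 to 5. These are accrual counts only. They do not show that a 7-day report would have paused enrolment.

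**The case against.** The strongest reply is that the exception has little to act on and that other rules already cover the deaths that matter.

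- *The term is never applied to metabolic disease.* The protocol calls these effects complications or consequences, and carcinoma known at entry is excluded. This stands in part: the reach of the exception is ambiguous, not established. An undefined term in a mandatory rule is still a defect.
- *Two expedited routes remain.* A reader might infer that such a death is bound to escape the 7-day report, or that continuing review is the only way the IRB would hear of it. The documents support neither. The death could qualify as an Unanticipated Problem on severity, and Section 6.3.1 requires immediate notice of a safety concern. If deferral caused the death, both could well apply. What remains is that each depends on the investigator's judgement.
- *The exception is not specific to an arm.* A disease-attributed death after adrenalectomy is equally exempt. This stands. The unevenness lies between causes of death. It bears on the comparison because Section 8.5 assigns surgical complications to one arm and worsening to the other.
- *Observation is short and monitored.* It lasts 6 months, with adrenal CT at months 3 and 6 (Section 3.3.2) and crossover for tumour growth or overt signs (Section 3.1). This limits the missed-malignancy scenario but does not affect a metabolic or cardiovascular death.
- *Sections 6.2.1 and 6.2.2 do not contradict each other.* An expedited rule and a periodic table may differ in scope, and no death is lost to the IRB altogether. This stands.

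**Conclusion.** The concern holds as a flaw in a stated safety rule. The exception is undefined, does not fit the trial population, and may release from the mandatory 7-day report a death attributed to the condition left untreated, while a surgical-complication death is always reported in that time. The remaining expedited routes are discretionary.

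The conclusion assumes that an investigator could reasonably apply the term to the condition under study, which the protocol's own account of its natural history allows but does not require.

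Its size cannot be fixed from the documents. A reader might take the coronary disease figures in Section 1.2 (26.3% versus 2.9%) as evidence that such deaths would be common. They are cross-sectional prevalences in 19 patients with subclinical hypercortisolism and 203 with nonfunctioning adenomas. They are not mortality, and they do not compare surgery with observation, so they say nothing about magnitude here.

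The sample size, the power statement and the primary analysis are unaffected. The change is still worth making because it is specific and nearly free.

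**What to change.** In Section 6.2.1, delete the exception for progressive disease so that all deaths on study are reported within 7 days regardless of attribution. The expedited rule would then take the same approach to attribution as Section 6.2.2 takes for Grade 5 events. Defining the term for this trial would be a weaker remedy, because classifying each death would still fall to the investigator.

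The cost is an amendment of a few words. All other deaths are already reportable within 7 days, so the only added reports are for deaths that would have been classed as progressive disease: at most a few over the trial. No treatment, endpoint, visit or analysis changes.

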6.2.2 NCI-IRB Requirements for PI Reporting at Continuing Review

The protocol PI will report to the NCI-IRB:

1. A summary of all protocol deviations in a tabular format to include the date the deviation occurred, a brief description of the deviation and any corrective action.
2. A summary of any instances of non-compliance
3. A tabular summary of the following adverse events:
 - All Grade 2 **unexpected** events that are possibly, probably or definitely related to the research;
 - All Grade 3 and 4 events that are possibly, probably or definitely related to the research;
 - All Grade 5 events regardless of attribution;
 - All Serious Events regardless of attribution.

Abbreviated Title: Subclinical Hypercortisolism

Version Date: 12/19/2016

NOTE: Grade 1 events are not required to be reported.

6.3 DATA AND SAFETY MONITORING PLAN

6.3.1 Principal Investigator/Research Team

The clinical research team will meet on a regular basis when patients are being actively followed on the trial to discuss each patient.

All data will be collected in a timely manner and reviewed by the principal investigator or a lead associate investigator. Adverse events will be reported as required above. Any safety concerns, new information that might affect either the ethical and or scientific conduct of the trial, or protocol deviations will be immediately reported to the IRB using iRIS.

The principal investigator will review adverse event and response data on each patient to ensure safety and data accuracy. The principal investigator will personally conduct or supervise the investigation and provide appropriate delegation of responsibilities to other members of the research staff.

7 STATISTICAL CONSIDERATIONS

The primary objective of this study is to determine if the use of unilateral adrenalectomy is associated with normalization and/or improvement of hypertension, diabetes, osteoporosis, hypercholesterolemia, and/or obesity compared to medical treatment-only arm.

Patients with subclinical hypercortisolism will be randomized to adrenalectomy or medical treatment as defined above and followed for 6 months. At the end of 6 months, the patients who were in the medical treatment-only arm will all be offered an adrenalectomy. Patients with subclinical hypercortisolism tend to have high prevalence of metabolic consequences, specifically hypertension, diabetes, obesity and/or osteoporosis.

To be conservative, the primary goal of this study will be to determine if the use of adrenalectomy is associated with 35% who have improvement vs. 5% who improve over 6 months without surgery as defined for any one or more of the following associated complications: hypertension, diabetes, osteoporosis, hypercholesterolemia, and/or obesity. With 31 patients per arm (62 total), there would be 80% power to detect a difference of this magnitude using a 0.05 significance level two-tailed Fisher's exact test.

For the potential 31 patients initially randomized to observation and then undergoing an adrenalectomy at 6 months, the level of MAP, systolic, and diastolic pressure at 6 months but just before surgery will be compared to these values in the potential 31 patients initially randomized to immediate adrenalectomy 6 months after surgery using a Wilcoxon rank sum test. In addition, in the patients initially randomized to observation the changes in MAP from baseline to 6 months of observation as well as the declines in systolic and diastolic pressure from 6 months of observation until 6 months after surgery will be compared with a Wilcoxon signed rank test. Other important continuous parameters such as change in weight, triglycerides, total, HDL and LDL cholesterol, A1c, fasting glucose, and bone density may also be compared within patients using Wilcoxon signed rank test.

Abbreviated Title: Subclinical Hypercortisolism

Version Date: 12/19/2016

It is expected that 15-20 eligible patients may be able to enroll on this trial per year. In order to enroll 62 evaluable patients, it is anticipated that 3-4 years would be required. In order to allow for a small number of inevaluable patients, the accrual ceiling will be set at 66 patients.

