2.4 RANDOMIZATION (OR STRATIFICATION) PROCEDURES

Patients with subclinical hypercortisolism will be randomized to adrenalectomy or observation as defined above and followed for 6 months. At the end of 6 months, the patients who were in the observation-only arm will all be offered an adrenalectomy. Patients with subclinical hypercortisolism tend to have high prevalence of metabolic consequences, specifically hypertension, diabetes, osteoporosis, hypercholesterolemia, and/or obesity. The patients will be randomized by the CRO.

To be conservative, the primary goal of this study will be to determine if the use of adrenalectomy is associated with 35% improvement vs. 5% improvement over 6 months without surgery as defined for any one or more of the following associated metabolic complications: hypertension, diabetes, osteoporosis, hypercholesterolemia, and/or obesity. With 31 patients per arm (62 total), there would be 80% power to detect a difference of this magnitude using a 0.05 significance level two-tailed Fisher's exact test.

Abbreviated Title: Subclinical Hypercortisolism**Version Date: 12/19/2016**

The following definitions will be used to determine if a given metabolic complication shows sufficient improvement in order to be considered as a component of a successful outcome:

Hypertension: normalization and/or improvement in blood pressure as assessed by reduction in pharmacotherapy and/or normalization of blood pressure (systolic pressure ≤ 140 and diastolic pressure ≤ 90) from baseline.

Diabetes: normalization and/or improvement in diabetes as assessed by normalization (A1C $< 6.5\%$), and/or reduction and/or discontinuation of pharmacotherapy.

Osteoporosis: an increase in the level of bone formation markers greater than the least significant change, which is calculated by multiplying the “precision error” of the specific biomarker by 2.77 (95% confidence interval) as per the National Osteoporosis Foundation (NOF) Clinician’s Guide to Prevention and Treatment of Osteoporosis 2013 ([Appendix D](#)).

Hypercholesterolemia: improvement in cholesterol as assessed by a reduction or elimination of pharmacotherapy and/or reduction in LDL levels to the optimal risk stratified goal as defined by ATP III guidelines ([Appendix E](#)).

Obesity: improvement in obesity as defined by a ten percent reduction in fasting morning weight compared to baseline.

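### With 31 evaluable patients per arm the planned Fisher test has a true size of at most 3.0%; Boschloo's test, ordered by the two-sided Fisher p-value, would raise power from 80.9% to 85.6%, and by less if the arms are unequal

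*Combined protocol and SAP*

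**What the plan says.** Section 7 frames the primary goal as detecting "35% who have improvement vs. 5% who improve over 6 months without surgery", where success is improvement in any one or more of five metabolic complications. The test is fixed in the statement that "there would be 80% power to detect a difference of this magnitude using a 0.05 significance level two-tailed" Fisher's exact test. Section 2.4 carries the same calculation: "With 31 patients per arm (62 total), there would be 80% power". Section 7 adds that, to allow for a few inevaluable patients, "the accrual ceiling will be set at 66 patients".

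Neither section mentions the actual size of the Fisher test at these numbers, or an unconditional exact alternative. Section 2.4 says that the central registration office will randomize. It does not describe blocking or any other device that would guarantee equal evaluable arms.

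**The concern.** Fisher's test conditions on the total number of responders. With 31 patients per arm, few distinct p-values are possible for each total, so the largest attainable p-value at or below 0.05 is often well below it. The plan judges its design by unconditional power at a 0.05 level, and on that same scale some of the level is left unused.

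There is little slack. With equal arms, 31 is the smallest number per arm from 30 upward that passes 80%; at 30 per arm Fisher has 78.8%. The observation arm is offered surgery at 6 months, so longer follow-up cannot restore the randomized comparison. A level-preserving gain in power that needs no extra patients is therefore worth having.

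**Working it through.** **Inputs** (Sections 2.4 and 7): n = 31 per arm; rates 0.35 (surgery) and 0.05 (observation); two-sided α = 0.05; Fisher's exact test.

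**Formulas.** Let x and y be responders on surgery and observation, b(k; n, π) the binomial probability, and R the set of tables (x, y) that the test rejects.
- Power = Σ over R of b(x; 31, 0.35) · b(y; 31, 0.05)
- Maximum size = max over π of Σ over R of b(x; 31, π) · b(y; 31, π), on a grid of π in steps of 0.001

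All 32 × 32 tables are enumerated.

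**Step 1: the plan's own figure.** With R = {two-sided Fisher p ≤ 0.05}, power is 0.8086. This reproduces the stated 80%.

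**Step 2: Fisher's true size.** The maximum is 0.0301, at π = 0.50. At lower common rates it is smaller still: 2.3% at 0.20, 1.0% at 0.10 and 0.17% at 0.05.

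**Step 3: Boschloo's test.** Order tables by the two-sided Fisher p-value and take the largest cutoff that keeps the maximum size at or below 0.05. The cutoff is 0.0732, with maximum size 0.0481 (at π about 0.41). Admitting the next table in the ordering would take the size to 0.0559. Power is 0.8561. Because the cutoff exceeds 0.05, every table that Fisher rejects is also rejected here.

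**Step 4: where the gain arises.** These are the tables added in the direction favouring surgery. As one example of their Fisher p-values, 7 v 1 gives 2 × [C(31,8) + 31 × C(31,7)] / C(62,8) = 2 × 89,405,550 / 3,381,098,545 = 0.0529.

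| Observation responders | Surgery responders needed: Fisher | Boschloo | Probability of the added table |
|---|---|---|---|
| 0 | 6 | 5 | 0.2039 × 0.0122 = 0.0025 |
| 1 | 8 | 7 | 0.3327 × 0.0547 = 0.0182 |
| 3 | 11 | 10 | 0.1336 × 0.1441 = 0.0193 |
| 4 | 12 | 11 | 0.0492 × 0.1482 = 0.0073 |
| 6 | 15 | 14 | 0.0032 × 0.0724 = 0.0002 |

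The sum is 0.0475, which equals 0.8561 − 0.8086. With 2 or 5 observation responders the two tests need the same count.

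**Step 5: other rates at 31 v 31.** For 30% v 5%, power goes from 65.6% to 72.6%. For 35% v 10%, it goes from 56.8% to 64.2%.

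**Step 6: other evaluable splits, 35% v 5%** (same enumeration, cutoff recomputed for each split; all figures in %).

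| Surgery v observation | Fisher maximum size | Fisher power | Boschloo power | Gain (points) |
|---|---|---|---|---|
| 31 v 31 | 3.01 | 80.86 | 85.61 | 4.75 |
| 33 v 33 | 3.56 | 84.23 | 88.52 | 4.28 |
| 30 v 31 | 3.97 | 86.11 | 89.21 | 3.10 |
| 31 v 30 | 3.97 | 81.58 | 85.55 | 3.97 |
| 30 v 32 | 3.96 | 86.75 | 88.65 | 1.90 |
| 32 v 30 | 3.96 | 83.92 | 87.56 | 3.64 |
| 29 v 33 | 4.16 | 84.27 | 86.42 | 2.15 |
| 33 v 29 | 4.16 | 86.03 | 87.61 | 1.58 |

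Boschloo's maximum size stays below 5% in every row, and its rejection region contains Fisher's in every row.

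**The case against.** **No error is shown.** Fisher's test is valid and prespecified, and the power claim is true. Choosing between conditional and unconditional inference is a matter of framework. The first part stands, and it limits this point to an improvement. The second carries less weight here, because Section 7 itself justifies the design by unconditional power at the 0.05 level.

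**The gain depends on exact balance.** This stands. Equal arms make Fisher unusually coarse. Moving one patient from surgery to observation (30 v 32) lifts its size to about 4.0% and its power to 86.8%, against 88.7% for Boschloo. A reader might infer from the equal-arm figures that Fisher could match 85.6% only by exceeding the 66-patient ceiling. That does not follow: Fisher reaches 86.1% at 30 v 31, which is 61 patients.

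**The two-sided version matters.** This also stands. Some software doubles a one-sided Boschloo p-value, as SciPy does. For 6/30 v 1/32, Fisher gives p = 0.0496 and the doubled version 0.058. At 30 v 32 the doubled version has 85.5% power, below Fisher's 86.8%. The guarantee of never doing worse than Fisher holds only for the ordering by the two-sided Fisher p-value.

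**A late change to a more liberal test can look opportunistic.** At 31 v 31 a Fisher p-value up to 0.073 would count as significant. The protocol version is dated 12/19/2016, and the documents do not say how far accrual had gone. Treatment is evidently not masked, and under Section 6.3.1 the principal investigator reviews response data on each patient. This is a reason to fix the change before any comparison by arm, and to document that.

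**Conclusion.** The point holds as an efficiency improvement. At 31 evaluable patients per arm and 35% v 5%, the specified Boschloo test gains 4.8 points of power at a maximum size of 4.8%. In the unequal splits examined the gain is 1.6 to 4 points. These figures rest on independent binomial outcomes and on the planning rates.

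Three stronger readings are not supported. The 80% claim is not wrong and type I error is not inflated. The 3.0% bound is not caused by low event rates, since it is reached at a common rate of 0.50. Nor does the change protect the trial against a control rate above 5%: at 35% v 10% power is still only 64.2%.

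**What to change.** In Sections 2.4 and 7, before outcome data are compared by arm, replace the named test with: *Boschloo's unconditional exact test, with tables ordered by the two-sided Fisher exact p-value (not by doubling a one-sided p-value), at a two-sided level of 0.05, computed for the actual evaluable numbers per arm.* State about 86% power for 35% v 5% at 31 per arm, and report Fisher's p-value as supportive.

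The sample size and the accrual ceiling need not change. The costs are a protocol amendment, a record that it was made without sight of results by arm, and a check that the software uses the stated ordering. Readers must also accept that the primary test can be significant when the familiar Fisher p-value is somewhat above 0.05.
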